9.5.3 Appropriateness of Measurements

All clinical assessments are standard measurements commonly used in studies of AD.

Standard safety assessments incorporated into this protocol include vital signs, clinical laboratory assessments, physical examinations, ECG measurements, and reports of AEs. MRI will be used to detect vasogenic edema, macrohemorrhage, an area of superficial siderosis, or a symptomatic microhemorrhage and is a standard evaluation to ensure subject safety. The C-SSRS has been endorsed by the FDA as a measure of potential suicidality ([Guidance for Industry Suicidality](#)).

A number of safety aspects have been built into the design of this study in light of the preclinical and clinical safety data with E2609, in addition to mitigating clinical risk in the progression from 14 days of dosing in the MAD study to 18 months of treatment in this Phase 2 study. Details are provided in [Section 9.2.6](#).

9.5.4 Reporting of Serious Adverse Events, Pregnancy, and Events Associated with Special Situations

9.5.4.1 Reporting of Serious Adverse Events

All SAEs, regardless of their relationship to study treatment, must be reported on a completed SAE form by email or fax as soon as possible but no later than 24 hours from when the investigator becomes aware of the event.

SAEs, regardless of causality assessment, must be collected up to 3 months after the last dose of study drug, ie, through to the final follow-up visit (Visit 20). (revised per Amendment 04) In subjects who discontinue study drug early, but continue with efficacy assessments, SAEs only need to be solicited up to 3 months after the last dose of study drug. However, any SAEs volunteered by subjects after this time point must be reported according to standard procedures. All SAEs must be followed to resolution or, if resolution is unlikely, to stabilization. Any SAE judged by the investigator to be related to the study treatment or any protocol-required procedure should be reported to the sponsor regardless of the length of time that has passed since study completion.

The detailed contact information for reporting of SAEs is provided in the Investigator Study File.

For urgent safety issues, please ensure all appropriate medical care is administered to the subject and contact the appropriate study team member listed in the Investigator Study File.

It is very important that the SAE report form be filled out as completely as possible at the time of the initial report. This includes the investigator's assessment of causality.

Any follow-up information received on SAEs should be forwarded within 1 business day of its receipt. If the follow-up information changes the investigator's assessment of causality, this should also be noted on the follow-up SAE form.

Preliminary SAE reports should be followed as soon as possible by detailed descriptions including copies of hospital case reports, autopsy reports, and other documents requested by the sponsor.

The investigator must notify his/her IRB/IEC of the occurrence of the SAE in writing, if required by their institution. A copy of this communication must be forwarded to the sponsor, or its designee, to be filed in the sponsor's Trial Master File.

9.5.4.2 Reporting of Pregnancy and Exposure to Study Drug through Breastfeeding

Any pregnancy in which the estimated date of conception is either before the last visit or within 28 days of last study treatment, or any exposure to study drug through breastfeeding during study treatment or within 28 days of last study treatment, must be reported.

If an adverse outcome of a pregnancy is suspected to be related to study drug exposure, this should be reported regardless of the length of time that has passed since the exposure to study treatment.

A congenital anomaly, death during perinatal period, an induced abortion, or a spontaneous abortion are considered to be an SAE and should be reported in the same time frame and in the same format as all other SAEs (see Reporting of Serious Adverse Events [[Section 9.5.4.1](#)]).

Pregnancies or exposure to study drug through breastfeeding must be reported by fax or email as soon as possible but no later than 1 business day from the date the investigator becomes aware of the pregnancy. The contact information for the reporting of pregnancies and exposure to study drug through breastfeeding is provided in the Investigator Study File. The Pregnancy Report Form must be used for reporting. All pregnancies must be followed to outcome. The outcome of the pregnancy must be reported as soon as possible but no later than 1 business day from the date the investigator becomes aware of the outcome.

A subject who becomes pregnant must discontinue study treatment.

9.5.4.3 Reporting of Events Associated with Special Situations

9.5.4.3.1 REPORTING OF ADVERSE EVENTS ASSOCIATED WITH STUDY DRUG OVERDOSE, MISUSE, ABUSE, OR MEDICATION ERROR

Adverse events associated with study drug overdose, misuse, abuse, and medication error refer to AEs associated with uses of the study drug outside of that specified by the protocol. Overdose, misuse, abuse, and medication error are defined as follows:

| | |
|------------------|--|
| Overdose | Accidental or intentional use of the study drug in an amount higher than the protocol-defined dose |
| Misuse | Intentional and inappropriate use of study drug not in accordance with the protocol |
| Abuse | Sporadic or persistent intentional excessive use of study drug accompanied by harmful physical or psychological effects |
| Medication error | Any unintentional event that causes or leads to inappropriate study drug use or subject harm while the study drug is in the control of site personnel or the subject |

All AEs associated with overdose, misuse, abuse, or medication error should be captured on the Adverse Event eCRF and also reported using the procedures detailed in Reporting of Serious Adverse Events ([Section 9.5.4.1](#)) even if the AEs do not meet serious criteria. Abuse is always to be captured as an AE. If the AE associated with an overdose, misuse, abuse, or medication error does not meet serious criteria, it must still be reported using the SAE form and in an expedited manner but should be noted as nonserious on the SAE form and the Adverse Event eCRF.

9.5.4.3.2 REPORTING OF STUDY-SPECIFIC EVENTS

Study-specific events (as detailed in [Section 9.5.1.5.2](#)) should always be considered serious important medical events and be entered on the Adverse Event eCRF and reported using the procedures detailed in Reporting of Serious Adverse Events ([Section 9.5.4.1](#)), even if the study-specific event does not meet other serious criteria.

9.5.4.4 Expedited Reporting

The sponsor must inform investigators (or as regionally required, the head of the medical institution) and regulatory authorities of reportable events, in compliance with applicable regulatory requirements, on an expedited basis (ie, within specific time frames). For this reason, it is imperative that sites provide complete SAE information in the manner described above.

9.5.4.5 Breaking the Blind

In the case of a medical emergency where the appropriate treatment of the subject requires knowledge of the study treatment given, the investigator may break the randomization code for an individual subject. In all such cases, the AE necessitating the emergency blind break will be handled as an SAE in accordance with the procedures indicated above. Any broken code will be clearly justified and documented. The medical monitor must be notified immediately of the blind break.

9.5.4.6 Regulatory Reporting of Adverse Events

Adverse events will be reported by the sponsor or a third party acting on behalf of the sponsor to regulatory authorities in compliance with local and regional law and established guidance. The format of these reports will be dictated by the local and regional requirements.

All studies that are conducted within any European country will comply with European GCP Directive 2005/28/EC and Clinical Trial Directive 2001/20/EC. All SUSARs will be reported, as required, to the competent authorities of all involved European member states.

9.5.5 Completion/Discontinuation of Subjects

A subject may elect to discontinue study drug or withdraw from the study at any time for any reason. All subjects who discontinue taking study drug prematurely for any reason will undergo an ED Visit within 7 days of their last dose of study drug (see [Section 9.1.2.2](#)). In addition, Follow-Up Visits will be scheduled 2, 4, 8, and 12 weeks after the last dose of study drug (Visits W2, 19, W8, and Visit 20, respectively) (see [Section 9.1.2.3](#)). (revised per Amendment 04) See [Table 7](#) for full details of the assessments to be performed at these visits. Subjects who discontinue study drug prematurely will also be scheduled to return to the study site for each scheduled visit when clinical efficacy assessments are to be conducted (ie, at Visits 11, 14, 15, 16, 17, and 18, if these visits have not already been performed). At these visits, only clinical efficacy assessments (MMSE, CDR, ADAS-cog14, FAQ, CBB and ISLT) will be conducted. Subjects who discontinue early from study drug are considered on study as long as they return for their regularly scheduled clinical efficacy visits as outlined above. Subjects who discontinue study drug early (as opposed to subjects whose dosing with study drug is temporarily suspended under Medical Monitor guidance) will not be permitted to restart study drug.

The investigator will promptly explain to the subject involved that the study will be discontinued for that subject and will provide appropriate medical treatment and other necessary measures for the subject. A subject who has ceased to return for visits will be followed up by mail, phone, or other means to gather information such as the reason for failure to return, the status of treatment compliance, the presence or absence of AEs, and clinical courses of signs and symptoms.

Subjects who withdraw prematurely from the study will be withdrawn for 1 of these primary reasons: AE(s), lost to follow-up, subject choice, inadequate therapeutic effect, withdrawal of consent, pregnancy, study terminated by sponsor, or other. In addition to the primary reason, the subject may indicate 1 or more secondary reason(s) for withdrawal from the study. Study disposition information will be collected on the Subject Disposition eCRF.

A subject removed from the study for any reason may not be replaced.

9.5.6 Abuse or Diversion of Study Drug

Adverse events associated with abuse or diversion will be appropriately reported as AEs and monitored per [Section 9.5.1.5.1](#). Abuse is always to be captured as an AE.

During the study, the investigator should be aware of the possibility of abuse or diversion of study drugs and should report any concern about mishandling, abuse, loss, theft, or diversion of study drugs by completing the Abuse or Diversion of Study Drug eCRF. (revised per Amendment 04)

9.5.7 Confirmation of Medical Care by Another Physician

The investigator will instruct subjects to inform site personnel when they are planning to receive medical care by another physician. At each visit, the investigator will ask the subject whether he or she has received medical care by another physician since the last visit or is planning to do so in the future. When the subject is going to receive medical care by another physician, the investigator, with the consent of the subject, will inform the other physician that the subject is participating in the clinical study.

9.6 Data Quality Assurance

This study will be organized, performed, and reported in compliance with the protocol, standard operating procedures, working practice documents, and applicable regulations and guidelines. Site audits will be made periodically by the sponsor's or the CRO's qualified compliance auditing team, which is an independent function from the study team responsible for conduct of the study.

9.6.1 Data Collection

Data required by the protocol will be collected on the eCRFs and entered into a validated data management system that is compliant with all regulatory requirements. As defined by ICH guidelines, the CRF is a printed, optical, or electronic document designed to record all of the protocol-required information to be reported to the sponsor on each study subject.

Data collection on the eCRF must follow the instructions described in the CRF Completion Guidelines. The investigator has ultimate responsibility for the collection and reporting of all

clinical data entered on the eCRF. The investigator or designee as identified on Form FDA 1572 (where applicable) must sign the completed eCRF to attest to its accuracy, authenticity, and completeness.

Completed, original eCRFs are the sole property of Eisai and should not be made available in any form to third parties without written permission from Eisai, except for authorized representatives of Eisai or appropriate regulatory authorities.

9.6.2 Clinical Data Management

All software applications used in the collection of data will be properly validated following standard computer system validation that is compliant with all regulatory requirements. All data, both eCRF and external data (eg, laboratory data), will be entered into a clinical system.

Electronic source (eSource) methodology may be used for some of the clinical efficacy assessments performed in this study.

9.7 Statistical Methods

All statistical analyses will be performed by the sponsor or designee. Statistical analyses will be performed using SAS software or other validated statistical software as required.

All statistical tests will be based on the 5% (2-sided) level of significance, except for the Bayesian methods on the primary endpoint.

9.7.1 Statistical and Analytical Plans

The statistical analyses of study data are described in this section. Further details of the analytical plan will be provided in the statistical analysis plan, which will be finalized before the first interim efficacy analysis.

9.7.1.1 Study Endpoints

See [Section 9.2.3](#) for a discussion of the rationale for the selection and clinical relevance of the primary study endpoint. Further information on the derived ADCOMS is described in [Section 9.5.1.3.1](#).

9.7.1.1.1 PRIMARY ENDPOINT

- Change from baseline in the derived ADCOMS at 18 months of treatment in MCI/Prodromal subjects

9.7.1.1.2 SECONDARY ENDPOINTS

Change from baseline in: (revised per Amendment 02)

- Total hippocampal atrophy at 12 and 18 months of treatment in MCI/Prodromal subjects as measured by vMRI
- The derived ADCOMS at 18 months of treatment in mild to moderate AD subjects (revised per Amendment 01)

9.7.1.1.3 EXPLORATORY ENDPOINTS

(revised per Amendments 01, 02, and 04)

Change from baseline in:

- The derived ADCOMS at 12 months of treatment in MCI/Prodromal and mild to moderate AD subjects
- Total hippocampal volume at 12 and 18 months of treatment in mild to moderate AD subjects as measured by vMRI
- CSF A β (1-x) and A β (1-42) after at least 4 weeks and at 18 months of treatment in MCI/Prodromal and mild to moderate AD subjects
- The following clinical assessments at 12 weeks and at 6, 9, 12, 15, 18, 19, and 21 months: ADAS-cog, CDR, MMSE, ISLT, CBB, and FAQ in MCI/Prodromal and mild to moderate AD subjects
- CSF biomarkers of neurodegeneration (eg, tau and p-tau) at 18 months of treatment in MCI/Prodromal and mild moderate AD subjects
- Plasma and CSF amyloid, and CSF BACE1 measurements after 4 weeks and 18 months of treatment, and during post-treatment follow-up in MCI/Prodromal and mild moderate AD subjects
- Left and right hippocampal, whole brain, and total ventricular volume at 6, 12, and 18 months in MCI/Prodromal and mild to moderate AD subjects as measured by vMRI
- Brain amyloid levels as measured by amyloid PET at 18 months in MCI/Prodromal and mild to moderate AD subjects
- The population PK parameters of E2609 including the effect of intrinsic and extrinsic factors (including *NAT2* phenotype) in MCI/Prodromal and mild to moderate AD subjects

9.7.1.2 Definitions of Analysis Sets

- The Randomized Set is the group of subjects who are randomized to study drug.
- The Safety Analysis Set is the group of subjects who receive at least 1 dose of study drug and have at least 1 postdose safety assessment.

- The Full Analysis Set (FAS) is the group of randomized subjects who receive at least 1 dose of study drug and have baseline and at least 1 postdose primary efficacy measurement.
- The Per Protocol (PP) Analysis Set is the subset of subjects in the FAS who sufficiently comply with the protocol. The PP Analysis Set will be used to conduct a sensitivity analysis of the primary efficacy endpoint. Details of the evaluability criteria will be determined before database lock and treatment unblinding, and will be specified in the statistical analysis plan.
- The PK Analysis Set is the group of subjects with at least 1 quantifiable E2609 plasma concentration accompanied by a documented dosing history.
- The PD Analysis Set is the group of subjects who have a baseline PD measurement and at least 1 posttreatment PD measurement.

9.7.1.3 Subject Disposition

The number of subjects screened, the number (percent) of subjects who failed screening, and the reasons for screen failure will be summarized, based on data reported on the Screening Disposition eCRF. The distribution of the number of randomized subjects enrolled by each site will be summarized for each randomized treatment group. The primary reasons for screen failures (did not meet inclusion or met exclusion criteria, AE, lost to follow-up, withdrawal of consent, and other) will be presented.

Study Completion: The number (percent) of randomized and treated subjects who completed the study and who withdrew from the study will be summarized according to the primary reason for discontinuation and secondary reason(s) for discontinuation, based on data reported on the Subject Disposition (Study Phase) CRF. The number (percent) will be presented by treatment group and total for subjects; randomized, not treated, treated, who completed the study, and withdrew from the study. The primary reasons for discontinuation from the study are: AE, lost to follow-up, subject choice, withdrawal of consent, pregnancy, study terminated by sponsor, and other. The secondary reasons for discontinuation from the study are: AE, subject choice, and other.

Completion of Study Treatment: The number (percent) of randomized and treated subjects who completed study drug and who discontinued from study drug will be summarized according to the primary reason for discontinuation and also according to secondary reason(s) for discontinuation, based on data reported on both the Subject Disposition (Study Phase) eCRF and ED from Study Drug eCRF. The number (percent) will be presented by treatment group and total for subjects; randomized, not treated, treated, who completed study drug, and discontinued from study drug. The primary reasons for discontinuation from the study drug are: AE, lost to follow-up, subject choice, withdrawal of consent, pregnancy, study terminated by sponsor, inadequate therapeutic response, and other. The secondary reasons for discontinuation from the study are: AE, subject choice, and other.

9.7.1.4 Demographic and Other Baseline Characteristics

Demographic and other baseline characteristics for the Safety Analysis Set and FAS will be summarized for each treatment group using descriptive statistics. Continuous demographic and baseline variables include age, MMSE and FAQ; categorical variables include sex, age group (≤ 65 years, age > 65 years), race, ethnicity, *ApoE4* status (positive or negative), prior treatment with AChEIs or memantine (no or yes), and clinical population (MCI/Prodromal AD or mild to moderate AD). (revised per Amendment 01)

9.7.1.5 Prior and Concomitant Therapy

All investigator terms for medications recorded in the eCRF will be coded to an 11-digit code using the World Health Organization Drug Dictionary (WHO DD) (Mar 2014 or higher). (revised per Amendment 04) The number (percentage) of subjects who took prior and concomitant medications will be summarized on the Safety Analysis Set by treatment group, Anatomical Therapeutic Chemical class, and WHO DD preferred term. Prior medications will be defined as medications that stopped before the first dose of study drug. Concomitant medications will be defined as medications that (1) started before the first dose of study drug and were continuing at the time of the first dose of study drug, or (2) started on or after the date of the first dose of study drug up to the date of the last dose. All medications will be presented in subject data listings.

Medications taken within the 12-week Follow-Up period will also be recorded.

9.7.1.6 Efficacy Analyses

The MCI/Prodromal Cohort

The study in the MCI/Prodromal cohort is based on Bayesian adaptive design. Frequent interim analyses will be performed to assess the probability of early success and futility and to make early stopping decisions. Response adaptive randomization will be used to update the randomization probability among treatment groups at each interim analysis. Key definitions relevant to the Bayesian aspects of the adaptive design are given below.

Study Definitions

- **Maximum Effective Dose (d_{Max}):** The dose that achieves the greatest treatment effect.
- **ED₉₀:** The lowest dose that achieves at least 90% of the d_{Max} treatment effect in the derived ADCOMS.
- **Early Success:** The study in the MCI/Prodromal cohort will meet early success criteria if the probability that the ED₉₀ at 18 months of treatment achieves 25% improvement over placebo is at least 80%. Early success is achieved before all MCI/Prodromal subjects complete 18 months of treatment and can only be determined after at least 200 MCI/Prodromal subjects have been randomized. If early success is declared before

full randomization, the randomization of new MCI/Prodromal subjects will stop but subjects already randomized into the study will receive the full 18 months of treatment (following confirmation from the Sponsor's Senior Management).

- **Futility:** The study in the MCI/Prodromal cohort will meet statistical futility criteria if the probability that the ED₉₀ is better than placebo by the clinically significant difference of 25% is less than 5% at 18 months of treatment. The statistical futility boundary is binding; if the statistical futility boundary is crossed the study will be considered to have failed.
- **Study Success:** The study in the MCI/Prodromal cohort will be considered a success if an ED₉₀ at 18 months treatment has at least an 80% probability of achieving 25% improvement over placebo at either an interim analysis or at the final analysis.

The Mild to Moderate AD Cohort (revised per Amendment 01)

All mild to moderate AD subjects will be included in the efficacy evaluations of the Mild to Moderate AD cohort. The analysis of the Mild to Moderate AD cohort is based on the group sequential design. Interim analyses in the Mild to Moderate AD cohort will only be performed after the MCI/Prodromal cohort crosses the early success boundary. The early efficacy signal based on the change from baseline of ADCOMS at 18 months is defined as crossing the interim-analysis boundaries for overwhelming efficacy in the mild to moderate AD population. The O'Brien-Fleming (OF) boundaries based on Lan-DeMets alpha spending function will be used to assess overwhelming efficacy. The corresponding OF boundaries based on *P* values will be 0.076, 0.0221, and 0.0423 for the first, second, and final analyses, respectively, according to 2 planned interim analyses at the 60% and 80% information fraction. (revised per Amendment 01)

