The Mild to Moderate AD Cohort (revised per Amendment 01): All mild to moderate AD subjects will be included in the efficacy evaluations of the Mild to Moderate AD cohort. The analysis of the Mild to Moderate AD cohort is based on the group sequential design. Interim analyses in the Mild to Moderate AD cohort will only be performed after the MCI/Prodromal cohort crosses the early success boundary. The early efficacy signal based on the change from baseline of ADCOMS at 18 months is defined as crossing the interim-analysis boundaries for overwhelming efficacy in the mild to moderate AD population. The O'Brien-Fleming (OF) boundaries based on Lan-DeMets alpha spending function will be used to assess overwhelming efficacy. The corresponding OF

boundaries based on P values will be 0.076, 0.0221, and 0.0423 for the first, second, and final analyses, respectively, according to 2 planned interim analyses at the 60% and 80% information fraction. (revised per Amendment 01)

Analysis for the primary endpoint

Primary analysis of primary endpoint

The primary analysis will be based on MCI/Prodromal subjects from the FAS with the prespecified censoring rule applied. The primary endpoint is the change from baseline to 18 months in the derived ADCOMS. The dose-response of the primary endpoint is modelled with a first-order normal dynamic linear model, where Normal and Inverse-Gamma priors are used. The primary efficacy analysis will calculate the Bayesian posterior probability that the dose identified is the most likely ED₉₀ dose that achieves 25% improvement over the placebo arm. At each interim analysis and the final analysis, 2 Bayesian probabilities will be summarized for each active dose: the probability it is the ED₉₀ dose and the probability of achieving 25% improvement over the placebo arm.

For the clinical efficacy data (ie, derived ADCOMS, MMSE, ADAS-cog, CDR, CBB, ISLT, and FAQ), subjects will be censored at the time of initiation of treatment with AChEIs or memantine, if they were not on these medications at the time of Baseline cognitive assessment (Visit 2), and will be censored at the time of dose adjustment of AChEIs or memantine if they were already on stable treatment with these medications at the time of Baseline cognitive assessment (Visit 2). The value of the primary endpoint for censored subjects will be imputed using data up to the censoring time and Bayesian longitudinal modeling.

Sensitivity analyses of primary endpoint

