If the predefined threshold for futility is reached, no additional subjects will be randomized into the study and the treatment of subjects already randomized into the study will stop and the study will be declared as "failed". All subjects will be monitored for safety for 3 months following their last dose.

If neither early success nor futility is reached and the study reaches full randomization, all subjects will complete 18 months of treatment. Interim efficacy analyses will be conducted every 3 months after full randomization is reached to assess futility and early success until all subjects complete 18 months of treatment. After full randomization, all study subjects will stop treatment only in the

event of futility.

The Mild to Moderate AD Cohort (revised per Amendment 01)

A group sequential design will be used for the Mild to Moderate AD cohort. This design includes 3 looks, 2 interim looks (when 60% and 80% information fractions are achieved) and 1 final look. Interim analyses will be performed after the MCI/Prodromal cohort crosses the early success boundary. The corresponding efficacy boundaries will be 0.076, 0.022, and 0.0423 for the first, second, and final analyses, respectively. If the actual information fraction during the interim analyses is different from 60% or 80% at the interim, the efficacy boundaries will be adjusted based on the actual information fraction. If early success in the MCI/Prodromal cohort is not achieved before the final analysis that is performed when all subjects have completed 18 months treatment, then only a final analysis will be performed in mild to moderate AD subjects. In the event of futility in the MCI/Prodromal cohort, an analysis will be performed for the Mild to Moderate AD cohort based on the data for mild to moderate AD subjects available at that time. (revised per Amendment 01)

Adaptive Randomization in the MCI/Prodromal Cohort

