The null and alternative hypotheses and the statistical test are the same as those for vMRI. To estimate the sample size for the amyloid PET imaging subgroup at 18 months, a common SD of the change from baseline was estimated at 0.33 and a reasonable mean difference between treatment and placebo was estimated as 0.25 (standardized uptake value ratio [SUVR]). Assuming a moderate dose-response, the best dose would achieve a difference of 0.25 (SUVR) and the middle and low doses would achieve a difference of 0.2 and 0.15 (SUVR), respectively; this would require a total of 100 subjects from all 4 arms at 18 months to achieve 80% power.

9.7.2.2 Sample Size Rationale for the Mild to Moderate AD Cohort (revised per Amendment 01)

ADCOMS at Month 18

The null hypothesis is that there is no difference between active dose and placebo. There are 2 null hypotheses corresponding to 2 active doses. The alternative hypothesis is that at least 1 null hypothesis is false. The null hypotheses will be tested using Dunnett's test with 2-sided alpha of 0.05 as described for the Mild to Moderate AD cohort in [Section 9.7.1.6.2](#). The statistical power was estimated through simulation for the dose-response assumption that the percent reduction in change from baseline of ADCOMS at 18 months compared with placebo would be 33% and 50% corresponding to the 2 doses, respectively. The estimated power for the actual planned 200 mild to moderate AD subjects is approximately 80% assuming a 2-sided alpha of 0.05. (revised per Amendment 01)

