A group sequential design will be used for the Mild to Moderate AD cohort. (revised per Amendment 01) This design includes 3 looks, 2 interim looks (when 60% and 80% information fractions are achieved) and 1 final look. The information fraction is the number of assessments in all treatment arms divided by the total number of expected assessments. Interim analyses will be performed after the MCI/Prodromal cohort crosses the early success boundary. The corresponding efficacy boundaries will be 0.076, 0.022, and 0.0423 for the first, second, and final analyses, respectively. If the actual information fraction during the interim analyses is different from 60% or 80% at the interim, the efficacy boundaries will be adjusted based on the actual information fraction.

If early success in the MCI/Prodromal cohort is not achieved before the final analysis that is performed when all subjects have completed 18 months treatment, then only a final analysis will be performed in mild to moderate AD subjects. In the event of futility in the MCI/Prodromal cohort, an analysis will be performed for the Mild to Moderate AD cohort based on the data for mild to moderate AD subjects available at that time. (revised per Amendment 01)

Randomization into the Mild to Moderate AD cohort will remain at a fixed schedule throughout Stage B. (revised per Amendment 01)

The interim analyses in the Mild to Moderate AD cohort will be conducted by an independent analysis group. (revised per Amendment 01)

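### The first interim efficacy boundary for the Mild to Moderate AD cohort is printed as P = 0.076; the stated design gives 0.0076, and the printed figure nearly doubles the type I error

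*Protocol*

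**What the plan says.** Section 9.7.1.6 puts the Mild to Moderate AD cohort on a group-sequential design for the 18-month change in ADCOMS. It states that O'Brien-Fleming "boundaries based on Lan-DeMets alpha spending function will be used to assess overwhelming efficacy", and that the P-value boundary "values will be 0.076, 0.0221, and 0.0423 for the first, second, and final analyses, respectively". Crossing an interim boundary is what defines an early efficacy signal in this cohort.

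Section 9.7.3 gives the timing: "This design includes 3 looks, 2 interim looks (when 60% and 80% information fractions are achieved) and 1 final look". It then repeats the thresholds with the second one rounded: "The corresponding efficacy boundaries will be 0.076, 0.022, and 0.0423 for the first, second, and final analyses, respectively". The synopsis carries the same figures under Efficacy Analyses ("boundaries based on P values will be 0.076, 0.0221, and 0.0423 for the first, second, and final analyses") and under Interim Analyses ("The corresponding efficacy boundaries will be 0.076, 0.022, and 0.0423 for the first, second, and final analyses").

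The error rate is two-sided 5%. Section 9.7 says: "All statistical tests will be based on the 5% (2-sided) level of significance, except for the Bayesian methods on the primary endpoint". Section 9.7.2.2, for this cohort, says: "The null hypotheses will be tested using Dunnett's test with 2-sided alpha of 0.05".

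Two conditions apply. The interim looks take place only once the MCI/Prodromal cohort has crossed its early success boundary. The boundaries are to be recalculated if the actual information fraction is not 60% or 80%.

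**The concern.** O'Brien-Fleming boundaries are strictest at the first look and relax towards the final one. The printed sequence does the opposite at its first step: 0.076 is looser than both 0.0221 and 0.0423, and it exceeds the 5% available to the whole cohort. A result at 60% information with P = 0.07 would count as overwhelming efficacy, although the same P value at the final analysis would fail.

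This figure is an operative threshold for one of the two secondary efficacy objectives (Section 8.2), in a study whose results are meant to guide the move to Phase 3 (Section 7). The same figure stands at all four places, and 0.0076 appears nowhere, so a reader cannot find the right value by comparing sections.

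**Working it through.** **Inputs**
- Overall alpha: 0.05, two-sided (Sections 9.7 and 9.7.2.2).
- Boundary family: O'Brien-Fleming-type Lan-DeMets spending (Section 9.7.1.6).
- Information fractions: t = 0.6, 0.8, 1.0 (Sections 9.7.1.6 and 9.7.3).
- Printed boundaries: 0.076 / 0.0221 / 0.0423.

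**Step 1: cumulative alpha spent**

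With 0.025 per tail, α(t) = 4[1 − Φ(z₀.₉₈₇₅/√t)], where z₀.₉₈₇₅ = 2.2414.
- t = 0.6: 2.2414/0.7746 = 2.894, so α = 0.00762
- t = 0.8: 2.2414/0.8944 = 2.506, so α = 0.02442
- t = 1.0: α = 0.05000

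**Step 2: solve for the boundaries**

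Under the null hypothesis the three test statistics are jointly standard normal with correlation √(tᵢ/tⱼ). The critical values c₁, c₂, c₃ satisfy:
- P(|Z₁| ≥ c₁) = 0.00762
- P(|Z₁| < c₁, |Z₂| ≥ c₂) = 0.02442 − 0.00762 = 0.01680
- P(|Z₁| < c₁, |Z₂| < c₂, |Z₃| ≥ c₃) = 0.05 − 0.02442 = 0.02558

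Recursive numerical integration gives:

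| Look | Information | z | Two-sided P | Printed |
|---|---|---|---|---|
| 1 | 60% | 2.669 | 0.00762 | 0.076 |
| 2 | 80% | 2.289 | 0.02210 | 0.0221 |
| Final | 100% | 2.031 | 0.04229 | 0.0423 |

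The second and third printed figures reproduce exactly, which identifies the method, sidedness and timing that were used. Both were solved on the basis that the first look had spent 0.0076, so the plan's own later figures imply 0.0076 for the first.

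**Step 3: could another method give 0.076?**
- One-sided 0.05, same spending family: 0.0114 / 0.0251 / 0.0410
- Two-sided test with the 0.05 spent as a single function (z₀.₉₇₅ in the formula): 0.0114 / 0.0244 / 0.0392
- Classic O'Brien-Fleming: 0.0085 / 0.0227 / 0.0416

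None does, and none matches the second and third figures either.

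**Step 4: type I error of each set, if all three looks are held**

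Probability under the null of first crossing at each look:

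| Set | Look 1 | Look 2 | Final | Total |
|---|---|---|---|---|
| 0.076 / 0.0221 / 0.0423 | 0.07600 | 0.00413 | 0.01658 | 0.09671 |
| 0.0076 / 0.0221 / 0.0423 | 0.00760 | 0.01682 | 0.02559 | 0.05001 |

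The ratio is 0.0967/0.0500 = 1.93. Monte Carlo with 2 million trials gave 0.0963 and 0.0497. A simulation of two doses against placebo with Dunnett-adjusted P values and equal allocation (1 million trials) gave 0.099 and 0.051.

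**Step 5: the second boundary**

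Using 0.022 in place of 0.0221, with the first look at 0.0076, gives a total of 0.04996. The difference between Sections 9.7.1.6 and 9.7.3 on this figure is rounding and does not matter.

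**The case against.** The case against concerns reach rather than the figure itself.

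- **The inflation is conditional.** Without early success in the MCI/Prodromal cohort there is a single analysis of this cohort, and 0.076 is never used. Section 9.7.2.1 puts a false success claim in MCI/Prodromal at no more than 5% when there is no dose effect. If the drug works in neither cohort, and assuming that the cohorts are independent and the single analysis is tested at 0.05, the overall error is at most about 0.05 × 0.0967 + 0.95 × 0.05 = 5.2%. This stands as a limit. The 9.67% applies when the looks are held and the drug has no effect in mild to moderate AD, for example when it works only in the earlier disease stage. That is a realistic case in which a false early signal here would mislead.
- **The boundaries are recalculated when the information fraction differs from plan.** Because the looks are triggered by an event in another cohort, an exact 60% look is not assured, and recalculation from the named function would remove 0.076. This mitigates the error but does not cure it. At exactly 60% the printed 0.076 stands, whereas at 61% the rule gives 4[1 − Φ(2.2414/√0.61)] ≈ 0.008. A tenfold fall for one extra point of information shows that the printed figure and the rule are incompatible.
- **The slip is conspicuous.** An analysis group working from the named spending function would obtain 0.0076. That is plausible, but the protocol prints an explicit number, and the document cannot show which value was programmed.
- **The consequence is bounded.** This is a secondary endpoint in a Phase 2 study. Crossing defines an early efficacy signal, and no statement was found that it stops the cohort. The Bayesian primary decision in MCI/Prodromal is unaffected. This is correct, and it limits the importance of the error, not its existence.

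**Conclusion.** The concern holds. Every element needed to fix the boundaries is in the protocol, and those elements give 0.0076 for the first look. No reading was found under which 0.076 is right.

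Used as printed, the boundary set has a two-sided type I error of 9.67% in place of 5.00%. The size rests on the looks falling at exactly 60%, 80% and 100% information, on both interim looks being held after MCI/Prodromal early success, and on the usual joint normality of the sequential statistics. If only the final analysis is run, the misprint has no effect. It is a wrong prespecified decision threshold and must be corrected before any interim look at this cohort.

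**What to change.** Replace 0.076 with 0.0076 at all four places: Section 9.7.1.6, Section 9.7.3, and the synopsis under Efficacy Analyses and under Interim Analyses. Have the independent analysis group confirm in writing that its program uses 0.0076 at 60% information, or the spending function directly. Writing 0.0221 for the second look in Section 9.7.3 and the matching synopsis text would be tidy but is optional.

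The cost is one figure corrected at four places in the next amendment. Sample size, look schedule, data collection and the other two boundaries do not change.
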